12.11 Safety Reporting to Investigators, IRBs, and Regulatory Authorities: The

Coordinating Center will be responsible for reporting all suspected unexpected serious adverse reactions (SUSARs) and any other applicable SAEs to regulatory authorities, investigators, and IRBs, as applicable. All SAEs will be reported to NIDA within 72 hours of the principal investigator becoming aware of the event. The Coordinating Center will also prepare an expedited report for other safety issues where these might materially alter the current benefit-risk assessment of a study drug or that would be sufficient to consider changes in the study drug administration or in the overall conduct of the trial. The study site also will forward a copy of all expedited reports to his or her IRB in accordance with local regulations.

The primary responsibility for monitoring data and safety will lie with the principal investigator ([name]), along with the site investigators and the research team. Each local investigator will meet with the research team at least once per week to discuss the safety of the study. The study principal investigator ([name]) will conduct a review of all adverse events upon completion of every study participant. The principal investigator will evaluate the frequency and severity of the adverse events and determine if modifications to the protocol or consent form are required.

As recommended the Serious Adverse Event Reporting and Tracking System (SAETRSII) will be used when reporting to NIDA.

- Actions of the Yale Human Investigations Committee will be reported to NIDA within 10 days of receipt of such correspondence from the Yale HIC.
- Changes or major amendments to the protocol will also be reported to the NIDA SO and PO for their approval prior to implementation.

13.0 UNANTICIPATED PROBLEMS

13.1 Definition of Unanticipated Problems: The Office for Human Research Protections (OHRP) considers unanticipated problems involving risks to participants or others to include, in general, any incident, experience, or outcome that meets all of the following criteria:

- Unexpected in terms of nature, severity, or frequency given (a) the research procedures that are described in the protocol-related documents, such as the Institutional Review Board (IRB)-approved research protocol and informed consent document; and (b) the characteristics of the participant population being studied;
- Related or possibly related to participation in the research ("possibly related" means there is a reasonable possibility that the incident, experience, or outcome may have been caused by the procedures involved in the research); and
- Suggests that the research places participants or others at a greater risk of harm (including physical, psychological, economic, or social harm) than was previously known or recognized.

13.2 Unanticipated Problem Reporting: The investigator will report unanticipated problems (UPs) to the reviewing Institutional Review Board (IRB) and to the Data Coordinating Center (DCC)/lead principal investigator (PI). The UP report will include the following information:

- Protocol identifying information: protocol title and number, PI's name, and the IRB project number;
- A detailed description of the event, incident, experience, or outcome;
- An explanation of the basis for determining that the event, incident, experience, or outcome represents an UP;
- A description of any changes to the protocol or other corrective actions that have been taken or are proposed in response to the UP.

To satisfy the requirement for prompt reporting, UPs will be reported using the following timeline:

- UPs that are serious adverse events (SAEs) will be reported to the IRB and to the DCC/study Coordinating Center within 48 hours of the investigator becoming aware of the event.
- Any other UP will be reported to the IRB and to the DCC/study Coordinating Center within 5 days of the investigator becoming aware of the problem.
- All UPs should be reported to appropriate institutional officials (as required by an institution's written reporting procedures), the supporting agency head (or designee), and the Office for Human Research Protections (OHRP) within 5 days of the IRB's receipt of the report of the problem from the investigator.]

14.0 STATISTICAL METHODS

All data obtained during the course of the study will be uploaded to an electronic database created by the Yale Center for Analytical Sciences (YCAS). Baseline and demographic data will be summarized for all treatment groups, and summary statistics will be provided by treatment group for the primary and all secondary outcomes. Treatment compliance measures and retention in treatment will be calculated by group and time and presented in tabular form. The full analysis set will be based on the modified Intent-To-Treat (ITT) principle, consisting of all participants who receive at least one dose of randomized study medication, and have a baseline and at least one post-baseline measurement. The per-protocol population will include all participants in the full analysis set but without any major protocol violations. Analyses of the perprotocol population will be considered secondary. The data will first be scanned for potential outliers. All outliers will be double-checked prior to analysis and as necessary, sensitivity analyses without outliers will be performed. Descriptive statistics (mean, standard deviation, range, frequency) will be computed for each variable first and presented in tabular form. Continuous variables will be checked for normality using normal probability plots and Kolmogorov-Smirnov tests. In case of non-normal distribution, transformations will be applied or non-parametric tests (226) will be used as necessary. A significance cutoff of 0.05 will be used to test the primary hypothesis whereas analyses of secondary outcomes will be adjusted using the Bonferroni-Holm procedure. Effect sizes and associated 95% confidence intervals will be calculated for the primary and all secondary outcomes in order to inform the design of future studies. All analyses will be performed in the latest version of SAS software.

supportive of our hypothesis. In addition to statistical testing, we will present least square mean estimates with 95% confidence limits for change from baseline by treatment group. We will also present estimates of treatment effects by site and baseline degree of cannabis exposure (high user or medium user) and evaluate whether treatment effects vary significantly by stratification factor (this assessment will be secondary to the primary evaluation of average treatment effects across strata). Other secondary and sensitivity analyses of the primary outcome include: (1) mixed model analysis with average number of times per day of self-reported consumption of cannabis or a cannabis containing product as the outcome, treatment group (active vs. placebo), site (4 levels), degree of cannabis exposure (medium, high) as between-participant factors, and time (baseline, first four weeks of the treatment period, last four weeks of the treatment period) as a within-participant factor; (2) tipping point analysis to assess sensitivity of conclusions to assumptions about missing data; (3) analyses of the per-protocol sample. In the mixed model analysis all available data on individuals will be used and the best fitting variancecovariance structure (among compound symmetry, compound symmetry heterogeneous, autoregressive of first order (AR(1)), autoregressive heterogeneous (ARH(1)), and unstructured) will be selected using Schwarz's Bayesian Criterion (BIC). Post-hoc analyses will provide information about treatment effect across the different time points, and the potential influence of the data collection site and baseline degree of cannabis exposure on the outcome trajectories. Additional exploratory analyses will be conducted to assess the effect of gender, desire to guit, lifetime cannabis use, tobacco use, alcohol use, and other drug use on the outcomes by including them into the models. Mixed models use all available data and are unaffected by data missing at random. Sensitivity analyses under missing not at random assumptions will also be performed.

14.2.2 Secondary Outcomes: The same analytic strategy will be followed for secondary outcomes compared to the primary outcome. Primary analyses will be based on ANCOVA with multiple imputation on the modified intent-to-treat sample, secondary analyses will include mixed models, tipping point analyses and analyses of the per protocol sample. The emphasis will be on effect estimation. Testing in the primary analyses will be adjusted using the Bonferroni-Holm method. For each eCB, plasma levels will be assessed by fitting a mixed effects model with treatment, time, site, and the interaction terms as fixed effects, and tobacco use as covariate. Exploratory analyses will be conducted to assess the effect of variables such as gender and use of other substances on endocannabinoids. Since we expect floor effects for the blood levels of PF-04457845 in the placebo condition, PF-04457845 blood level will be assessed by using non-parametric models (226, 227) with treatment, time, site, and the interaction terms as factors.

14.3 Safety Analysis: The review and summary of safety will be performed on the modified intent-to-treat sample. Events or abnormalities will be searched from the time of the first dose until 5 half-lives after the last dose. Clinical laboratory data will be summarized quantitatively using descriptive statistics such as changes from baseline summarized by mean, standard deviation, median, minimum and maximum, and summarized qualitatively by tabulating clinical abnormalities. Vital signs, BMI, weight will be summarized using descriptive statistics. Group differences in the percentage of participants who report AEs or exhibit clinically significant changes during 1) 8-week treatment phase (from the first dose until the last dose), and 2) the 4-week follow up phase (to assess any lingering post treatment safety issues) will be summarized in tabular form and presented. Data permitting, exploratory analyses may be performed to evaluate the statistical significance of between-group differences (e.g. using Fisher's exact tests for adverse events, t-tests or non-parametric equivalent for changes in continuous measures) and evaluation of the effects of duration of drug exposure or drug dose on any adverse events (e.g. using exact logistic regression) and laboratory measures (e.g. using mixed effects models).

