- 9) Polymorphism of relevant genes (e.g., FAAH gene) will moderate the change in cannabis use with PF-04457845 treatment
- 10) Over 8 weeks plasma endocannabinoid levels will be higher with PF-04457845 compared with placebo.
- 11) To evaluate the PD (plasma anandamide), and PK/PD relationships of PF-04457845.
- 12) To correlate changes in exposure to PF-04457845 and clinical response.
- 13) To correlate changes in plasma anandamide levels with clinical response to PF-04457845.
- 14) Change in serum levels of soluble biomarkers, such as inflammatory mediators, and their relationship to participant characteristics and change in study assessments.
- To determine whether over the 8 weeks of treatment 4 mg PF-04457845 QD weeks is superior to placebo in reducing sleep disturbances measured by:
 a. sleep report guestionnaires,
- 16) To evaluate the safety and tolerability of 4 mg PF-04457845 QD x 8 weeks in cannabis use disorder patients:
 - a. % of participants who meet the markedly abnormal criteria for safety electrocardiogram parameters at least once post-dose.
 - b. % of participants with treatment-emergent suicidal ideation or suicidal behavior as measured using the Columbia-Suicide Severity Rating Scale (C-SSRS).

Table 10: Primary and Secondary Objectives, Measures, and Endpoints

			bjectives, Measures, and Endpoints	
	Objective/s	Instrument/s	Endpoint/s	Outcome/s
Primary	To determine whether PF-04457845 is superior to placebo in reducing self- reported frequency of cannabis use.	TLFB	Change from baseline in the average number of times per day of self-reported consumption of cannabis or a cannabis containing product.	Differences between groups in the change from baseline use (2 weeks prior to randomization) in the average number of times per day of self-reported consumption of cannabis or a cannabis containing product in the last 4 weeks of the treatment.
		Self-report	% of participants who experience at least 1 treatment-emergent adverse event.	% who self-reported AEs or exhibited clinically significant
	To determine the safety and tolerability of 4 mg PF-04457845 QD x 8 weeks in cannabis use disorder patients.		% of participants who meet the markedly abnormal criteria for safety laboratory tests at least once post-dose.	changes during 1) 8-week treatment phase (from the first dose until the last dose), and

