8.0 STUDY INTERVENTION DISCONTINUATION AND PARTICIPANT DISCONTINUATION/WITHDRAWAL

8.1 Discontinuation of Study Intervention: Discontinuation from PF-04457845 does not mean discontinuation from the study. Attempts will be made to complete the remaining study procedures as indicated by the study protocol. If a clinically significant finding is identified (including, but not limited to changes from baseline) after enrollment, the investigator or qualified designee will determine if any change in participant management is needed. Any new clinically relevant finding will be reported as an adverse event (AE). Every attempt should be made to collect the data that would be collected at a termination visit (Week 9 Visit) as listed in 1.5 Schedule of Procedures: Table 2. If the participant is prematurely withdrawn from the treatment phase, he/she may be entered into the 4-week follow up phase.

8.2 Participant Discontinuation/Withdrawal from the Study: Participants are free to withdraw from participation in the study at any time upon request. The investigator may discontinue a participant's study participation at any time during the study if the participant meets the study termination criteria. In addition, a participant may discontinue his or her participation without giving a reason at any time during the study.

8.2.1 Criteria for Discontinuation or Withdrawal of a Participant: The primary reason for discontinuation or withdrawal of the participant from the study or study drug should be recorded using the following categories.

- 1) Adverse Event: The participant has experienced an AE that requires early termination because continued participation imposes an unacceptable risk to the participant's health or the participant is unwilling to continue because of the AE.
- 2) *Important Protocol Deviation*: The discovery post-randomization that the participant failed to meet protocol entry criteria or did not adhere to protocol requirements, and continued participation poses an unacceptable risk to the participant's health.
- 3) *Lost to Follow-Up*: The participant did not return to the study site and multiple attempts to contact the participant were unsuccessful. Attempts to contact the participant must be documented.

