9.9 *Early Termination Study Visit:* If a participant decides to withdraw from the study after randomization or is terminated by the site principal investigator for any reason after randomization, an early termination study visit will be conducted to close out the participant from the study. At this visit the participant will be instructed to return all unused study medication. The Week 9 procedures will be attempted at an early termination visit, which will be conducted per Section 9.7.1, both in person and remotely.

10.0 ASSESSMENTS:

Every effort should be made to ensure that protocol-required tests and procedures are completed as described. When a protocol-required test cannot be performed, study staff will be instructed to document the reason for the missed test and any corrective and preventative actions which s/he has taken to ensure that required processes are adhered to as soon as possible. Any protocol deviations should be documented in the study log.

10.1 Blood: Total blood sampling volume for the individual participants is approximately 420 mL over approximately 14 weeks of the study. The actual times of blood sampling may change. Additional blood samples may be taken for safety assessments at times specified by the Coordinating Center, provided the total volume taken during the study does not exceed 450 mL (safety, PF-04457845 levels, endocannabinoid levels).

10.2 Safety:

10.2.1 Laboratory Tests: The following safety laboratory tests will be performed at the following study visits: Screening, Week 1, Week, 5, Week 7, Week 9, and End of Study Visit (end of Week 12). They are conducted periodically throughout the duration of the study to monitor electrolyte and liver/kidney function. Additional laboratory results may be generated on the samples (without additional blood volume drawn) as a result of the method of analysis, the type of analyzers used, or as derived or calculated values; if such results are available, they may also be reported. Unscheduled clinical labs may be obtained at any time during the study to assess any perceived safety concerns.

Hematology: Hemoglobin, Hematocrit, RBC Count, MCV, MCHC, RDW, MCH, MPV, Platelet Count, WBC Count, Total Neutrophils (Abs), Eosinophils (Abs), Monocytes (Abs), Basophils (Abs), Lymphocytes (Abs); Collected using one 10cc Lavender-top Tube (tube contains EDTA as an anticoagulant).

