12.1 Reporting Period: For SAEs, the active reporting period begins from the time that the participant provides informed consent, which is obtained prior to the participant's participation in the study, through the last follow up visit (end of study visit). Should an investigator be made aware of any SAE occurring any time after the active reporting period, it must be promptly reported.

12.2 Capturing Adverse Events: Safety and adverse events will be captured using the Systematic Assessment for Treatment Emergent Events (SAFTEE) general and specific inquiry forms, which take approximately 20 minutes to administer. Collection of adverse events will commence from the time the participant signs the informed consent to participate in the study and will continue until the last safety follow up visit. At each study visit, the investigator will

assess whether any subjective AEs have occurred. A neutral question, such as "How have you been feeling since your last visit?" may be asked. Participants may report AEs occurring at any other time during the study. All participants experiencing AEs, whether considered associated with the use of the study drug or not, must be monitored until the symptoms subside and any clinically relevant changes in laboratory values have returned to Baseline or until there is a satisfactory explanation for the changes observed. All AEs will be documented, whether or not the investigator concludes that the event is related to the drug treatment. Any medical condition that is present at the time that the participant is screened will be considered as baseline and not reported as an AE. However, if the study participant's condition deteriorates at any time during the study, it will be recorded as an AE.

The following information will be documented for each event:

- 1. Event term.
- 2. Start and stop date and time.
- 3. Pattern of AE (Frequency).
- 4. Intensity.
- 5. Investigator's opinion of the causal relationship between the event and administration of study drug(s) (related or not related).
- 6. Investigator's opinion of the causal relationship to study procedure(s), including the details of the suspected procedure.
- 7. Action concerning study drug.
- 8. Outcome of event.
- 9. Seriousness.

The different categories of intensity (severity) are characterized as follows:

- Mild: The event is transient and easily tolerated by the participant. The event does not
 generally interfere with usual activities of dailyliving.

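### Safety is summarised on the modified ITT sample, so a dosed participant with a known event but no qualifying post-baseline measurement would be left out of the planned safety tables

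*Combined protocol and SAP*

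**What the plan says.** Section 14.3 fixes the population for all safety work: "The review and summary of safety will be performed on the modified intent-to-treat sample". The only definition of that sample is in the opening paragraph of Section 14.0, where the full analysis set is described as "consisting of all participants who receive at least one dose of randomized study medication, and have a baseline and at least one post-baseline measurement". The only other set is a subset of it: "The per-protocol population will include all participants in the full analysis set but without any major protocol violations". No set of all dosed participants is defined anywhere.

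The next sentence of Section 14.3 sets the time window: "Events or abnormalities will be searched from the time of the first dose until 5 half-lives after the last dose". Section 12.2 sets the collection rule: "All AEs will be documented, whether or not the investigator concludes that the event is related to the drug treatment". Safety and tolerability is the first-listed secondary endpoint in Section 4.2.2, and Table 10 expresses it as the percentage "of participants who experience at least 1 treatment-emergent adverse event", with parallel percentages for markedly abnormal laboratory and vital-sign values after dosing.

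**The concern.** The collection rule and the time window both start from exposure. The analysis set adds a condition that exposure does not guarantee. A participant can take drug, have an event that the site learns about, and give no further measurement. The event is then recorded but the person is not in the tables.

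The documents allow this to happen. Section 12.2 accepts adverse events reported at any time during the study. Section 12.9 foresees a site learning late of a serious event because the participant was treated elsewhere. Appendix H says the daily video calls are not meant for adverse event assessment but that a volunteered event is to be captured, and its call record lists dosing fields only.

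At stake is the numerator and denominator of a secondary endpoint. If people who leave with no further data have events more often than those who stay, the tabulated percentages are too low. If this happens more often in one arm, the comparison between arms is biased as well.

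**Working it through.** **Which participants fall between the two rules.**

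| Rule | Place | Dosed, known event, no qualifying later measurement |
|---|---|---|
| Events are recorded regardless of cause | 12.2 | Captured |
| Window opens at first dose | 14.3 | Inside |
| Needs a post-baseline measurement | 14.0, applied by 14.3 | Outside |

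The baseline condition excludes almost nobody, because timeline follow-back, laboratory tests, vital signs and ECG are all scheduled at screening. The post-baseline condition is the one that matters.

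**What counts as a measurement.** Section 14.0 ties the word to no variable. If a completed SAFTEE form counts, most participants with a collected event stay in. If only a cannabis-use record counts, someone whose event became known outside a visit or a completed follow-back call drops out.

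**The plan's own figures.** Section 14.1 gives d = 0.42, 80% power, two-sided alpha 0.05 and about 25% dropout.
- Per arm: 2 × (1.960 + 0.842)² / 0.42² = 89.0, so 178 in total, as stated.
- Inflated: 178 / 0.75 = 237.3, against 237 stated.

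Both reproduce, and neither depends on the safety set.

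**How large the loss could be.** The documents give no rate of dosed participants without a post-baseline measurement. Assume that dropout accrues at a constant weekly rate over 8 weeks.
- At 25%: 1 − 0.75^(1/8) = 3.5% leave in week 1; × 237 = 8.4, × 260 = 9.2.
- Section 5.2 goes from 260 randomised to 178 completing, which is 31.5% attrition: 1 − (178/260)^(1/8) = 4.6%; × 260 = 12.0.

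These figures count everyone assumed to leave in week 1. Those without a qualifying measurement are some part of that number, possibly none.

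**What such a loss would do to a table.** This is an illustration under assumptions: 130 dosed in one arm, every excluded person had the event, and about 5% of the rest did (6 events).

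| Excluded from the arm | All dosed | Modified ITT |
|---|---|---|
| 1 | 7/130 = 5.4% | 6/129 = 4.7% |
| 3 | 9/130 = 6.9% | 6/127 = 4.7% |
| 4 | 10/130 = 7.7% | 6/126 = 4.8% |
| 6 | 12/130 = 9.2% | 6/124 = 4.8% |

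This is a worst case by construction, since every excluded person is given an event.

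**Laboratory and vital-sign percentages.** Section 10.2.1 schedules the next safety laboratory test after Week 1 at Week 5. Under the constant rate, 1 − 0.75^(4/8) = 13.4%, about 35 of 260, would leave before it, fewer if early-termination samples are obtained. If all dosed participants were the denominator here, those never tested would count as not abnormal. One denominator therefore cannot serve every safety endpoint.

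**The case against.** The strongest reply is that few people are affected. Section 8.1 says "Discontinuation from PF-04457845 does not mean discontinuation from the study", and those withdrawn from treatment may enter the 4-week follow-up. Section 9.9 says "The Week 9 procedures will be attempted at an early termination visit". Calls run Monday to Friday and include a brief cannabis follow-back. Someone never reached again usually has no known event, so no analysis set would show one. All of this stands, and it is why the size is put at 0 to a few percent.

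It is also true that a person with no post-dose sample contributes no laboratory change in any population, so the harm falls mainly on adverse event and C-SSRS summaries. Serious events still go to the Coordinating Center within 24 hours (12.9) and to NIDA within 72 hours (12.11). The DSMB sees unblinded safety data (16.5), and the stopping rules in 8.4 name no analysis set.

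A reader might infer more than the documents support:
- *That everyone who stops soon after first dosing disappears.* Anyone who gives a qualifying later measurement stays in.
- *That 8 or 9 exposed people will be missing.* That is all assumed week-1 dropout.
- *That measurement means the primary outcome, so that anyone leaving before the last 4 treatment weeks is excluded.* Section 14.2.1 plans multiple imputation of outcome data, which would have little purpose if members had to have that outcome observed. The text does not rule the reading out, but does not favour it.
- *That participants are grouped by randomised arm.* This follows only from the ITT label; Section 14.3 is silent.
- *That early intolerance is a main cause of missing data, or that class toxicity raises the stakes.* The documents report no serious events and no group difference in minor event rates in the pilot (3.4.9). The FDA statement in 11.1.1 says the other compound's toxicity does not extend to the class.

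None of these limits supplies a safety population, so the gap in the rule remains.

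**Conclusion.** The point holds in a limited form. As written, Section 14.3 can leave out of the planned safety tables a dosed participant with a known adverse event, serious adverse event or C-SSRS event who has no qualifying later measurement. The number affected cannot be taken from the documents. It runs from 0 to a few percent (at most 3.5% to 4.6% for week-1 leavers), resting on constant weekly dropout and on how the undefined measurement is read. If dropout were concentrated at the start, the upper end would rise.

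The direction of any bias depends on whether those excluded had more events, and in which arm; the documents settle neither. Safety reporting during the trial, the sample size and the primary analysis are untouched, and safety testing is exploratory. Severity: should fix.

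**What to change.** In Section 14.3, replace the population sentence with wording such as: *Safety will be summarised in all randomised participants who took at least one dose of study medication, grouped by treatment actually received, regardless of whether any post-baseline measurement exists.*

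Then:
- use that set as the denominator for adverse event and serious adverse event percentages, in Section 4.2.2 and Table 10 as well;
- for laboratory, vital-sign, ECG and C-SSRS percentages, use dosed participants with at least one post-dose assessment of that type, and report by arm how many were not assessed;
- keep modified ITT for efficacy, and state in Section 14.0 which measurement its definition refers to.

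The cost is a few sentences, one population flag and a count of those not assessed for each assessment type. No new data are needed, and 178 and 237 do not change. It should be settled before unblinding, so that the safety denominator is not chosen with results in view.
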